5.1.15 QoL Questionnaires

FACT-G, EQ-5D, FKSI, Cost Effectiveness questionnaire: These forms will be referred to collectively as QoL Questionnaires and will be collected prior to first Nivolumab dose and at specific time-points as indicated in section 5.4

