5.3 Follow-up Procedures

- For patients who are still receiving Nivolumab:

Subject will be followed every 8-12 weeks starting from the date of registration for the first two years. , then every four-six months thereafter for five years or death, whichever comes first. The following procedures will be performed at each follow up:

- Physical exam (recommended), Performance Status (recommended), Vital Signs, Medication Review, AE assessment
- HR-QoL questionnaire at baseline, and then at six month intervals until patient meets primary endpoint
- Blood collection for correlative immunologic studies (see section 9.0): In total, all patients will get blood draws for correlative studies at baseline, follow up q 8-12 weeks (until discontinued or within first year of enrollment, whichever is first) and at 1 year (if discontinued before 1 year).
- Radiographic imaging: Tumor assessments will be completed by the investigator using the RECIST and ir-RECIST criteria as above.
 - CT chest, abdomen and pelvis with IV contrast (contrast recommended), if allowable by renal function. MRI with contrast (contrast recommended) can replace CT.
 - MRI, if necessary to confirm CT findings, at the discretion of physician

- For patients who have been discontinued from Nivolumab (See Section 4.3): Subject will be followed within 3 months from last dose ((+/- 2 months), or may be on date of discontinuation).

The following procedures will be performed:

- Physical exam (recommended), Performance Status (recommended), Vital Signs, Medication Review, AE sssessment
- Subsequent anti-cancer treatment/s
- Blood samples for correlation immunologic studies

After that, survival visits/phone calls continue annually to include Survival Status, AE Assessment, and Subsequent anti-cancer treatment/s.

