6.2 Safety/tolerability

Analyses will be performed for all subjects having received at least one fraction of SABR and one cycle of Nivolumab. The study will use the CTCAE version 4.0 for reporting of non-hematologic adverse events (<http://ctep.cancer.gov/reporting/ctc.html>) and modified criteria for hematologic adverse events.

6.3 Quality of Life (QoL)**6.3.1 Functional Assessment of Cancer Therapy-P (FACT-G) and Kidney Symptom Index (FKSI)**

Patient-reported functional status will be assessed the Functional Assessment of Cancer Therapy-General (FACT-G) (See appendix E). The FACT-G is a 28-item questionnaire that uses 5-point Likert-type response choices (0 = not at all; 1 = a little bit; 2 = somewhat; 3 = quite a bit; 4 = very much). It will take less than 10 minutes to complete the questionnaire. The Trial Outcome Indices (TOI) also will be utilized to measure the summed functional well-being, and physical well-being [102, 103]. A 5-point deterioration in the FACT-G TOI between pre-treatment and at post treatment or at year 1 will be considered clinically significant [104].

The FKSI is a 15 question validated symptom index for kidney cancer patients which has been used in several metastatic renal cell cancer studies [105]. This scale focuses on symptoms predominantly related to kidney cancer such as energy, fatigue, pain, bone pain, weight loss, shortness of breath, cough, fever, hematuria. This subscale of the FKSI-DRS was validated in another study as well [106]. The FACT-G and FKSI will

be collected prior to first Nivolumab dose (baseline), and at every subsequent follow up appointment until the patient meets primary endpoint [105][3][82].

The first analysis of change in QOL from baseline to 8 weeks will only be performed on patients who are still alive at 8 weeks. Changes in QOL will be also analyzed using all available data at baseline, 2, 4, 6, 8, 10 and 12 months with semiparametric generalized estimating equations (GEE).

Additionally, similarly we will also compare the percentage of patients with an effect size for the change in FKSI (FKSI) scores between pre-treatment and post treatment which will allow us to compare the percentage of patients whose functional status remains more similar to baseline levels.

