6.3.2 EQ-5D

The EQ-5D is a patient self-administrated questionnaire that takes approximately 5 minutes to complete (See appendix D). The first part consists of 5 items covering 5 dimensions including: mobility, self-care, usual activities, pain/discomfort, and anxiety/depression. Each dimension can be graded on 5 levels. Health states are defined by the combination of the leveled responses to the 5 dimensions, generating 243 health states to which unconsciousness and death are added.

The 5-item index score is transformed into a utility score between 0, "Worst health state," and 1, "Best health state." The index score or the cost-utility equation can be used in the quality adjusted survival analysis depending on the health state(s) of interest.

Additionally the EQ 5D is utilized to establish health state utility which is used in cost-effectiveness analysis to calculate quality adjusted life years. This is the recommended health state utility form used in the United Kingdom and approved by the National Institute for Clinical Excellence (NICE) and has been used to establish health state utility and metastatic renal cell cancer patients. The EQ 5D will be given at baseline and at follow ups. The EQ-5D will also be available in the Spanish language.

The EQ-5D also includes a visual analog scale (VAS), a validated measure of general well-being, scored on a scale of 0-100. These data will be analyzed over time in a similar manner as the FACT-G and FKSI. EQ-5D will be collected prior to first Nivolumab dose (baseline), and at every subsequent follow up appointment until the patient meets primary endpoint.

6.4 Cost effectiveness data collection:

Healthcare utilization data needed to assess costs will be obtained from insurance claims and medical records. Also the cost effectiveness questionnaire will be completed by the patients at baseline, 8 week follow up and 6 months follow up (see Appendix G). These costs will be divided into the following domains:

Hospitalizations: For hospitalizations with physician billing records, inpatient physician costs will be estimated by applying Medicare payment rates under the RBRVS-based Medicare Fee Schedule to billed procedures in the physician billing records.

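### Quality-of-life forms are six-monthly in sections 5.3 and 5.4 but due at every follow-up visit in 6.3, and collection ends at an event not defined for a patient, so the planned analyses may lack the forms they need

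*Combined protocol and SAP*

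**What the plan says.** **Timing.** Section 5.1.15 says the forms "will be collected prior to first Nivolumab dose and at specific time-points as indicated in section 5.4". The 5.4 footnote gives baseline and six-month intervals. Section 5.3, under patients still receiving nivolumab, gives "HR-QoL questionnaire at baseline, and then at six month intervals until patient meets primary endpoint". Section 6.3.1 says FACT-G and FKSI will "be collected prior to first Nivolumab dose (baseline), and at every subsequent follow up appointment until the patient meets primary endpoint", and 6.3.2 says "EQ-5D will be collected prior to first Nivolumab dose (baseline), and at every subsequent follow up appointment until the patient meets primary endpoint". Follow-up visits are 8-12 weeks apart in the first two years (5.3). Section 10.1 refers to baseline and later follow-ups without an interval, which leans towards 6.3.

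**Analyses.** Section 6.3.1 states "The first analysis of change in QOL from baseline to 8 weeks will only be performed on patients who are still alive" at that time, then "Changes in QOL will be also analyzed using all available data at baseline, 2, 4, 6, 8, 10 and 12 months" by GEE, and adds "A 5-point deterioration in the FACT-G TOI between pre-treatment and at post treatment or at year 1 will be considered clinically significant". Section 10.3 interpolates EQ-5D utility between visits and integrates it over survival time, up to the cost limit, which is one year in the primary analysis of 10.2.

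**After progression or discontinuation.** Section 4.4 releases patients with progressive disease from strict adherence to the study calendar. For patients off nivolumab, 5.3 provides one visit and then: "After that, survival visits/phone calls continue annually to include Survival Status". Neither list includes a quality-of-life form.

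**The concern.** Two schedules are in force at once, and the one in the Time and Events Table cannot supply the analyses in 6.3.1. Forms that were not collected cannot be recovered at analysis.

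The stopping event adds a second problem. The primary endpoint is a response rate, a property of the group, so a patient cannot meet it as written. Read as response, the rule contradicts 5.4, whose follow-up columns are headed as being for responders and mark the forms through month 60. Read as progression, forms cease when patients worsen. Later FACT-G, FKSI and EQ-5D values, including the year-1 TOI comparison, would then come mainly from patients who have not progressed.

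Third, quality-adjusted survival needs utility for the whole of year 1. A non-responder who stops nivolumab before month 6 may have only a baseline EQ-5D, and 10.3 gives no rule for utility after the last form.

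**Working it through.** **1. Scheduled forms against the planned times.** The required post-baseline times are week 8, and months 2, 4, 6, 8, 10 and 12 for the GEE (6.3.1). One month is taken as 52/12 = 4.33 weeks. The documents give no visit window, so ±1 month is my assumption.

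| Rule | Form times in year 1 (months) | GEE times covered within ±1 month |
|---|---|---|
| 5.3/5.4, six-monthly | 6, 12 | 2 of 6 |
| 6.3, every 8 weeks | 1.85, 3.69, 5.54, 7.38, 9.23, 11.08 | 6 of 6 |
| 6.3, every 9 weeks | 2.08, 4.15, 6.23, 8.31, 10.38, 12.46 (just past month 12) | 6 of 6 |
| 6.3, every 10 weeks | 2.31, 4.62, 6.92, 9.23, 11.54 | 5 of 6 |
| 6.3, every 12 weeks | 2.77, 5.54, 8.31, 11.08 | 4 of 6 |

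Under 5.3/5.4 nothing is scheduled at week 8 or at months 2, 4, 8 and 10. Under 6.3 with 12-week visits there are four forms for six times and none at week 8.

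**2. Stopping event read as progression (illustration only).** Inputs: historical median PFS of 4-4.6 months on nivolumab alone (1.4.2), 19 patients (11.2), first post-baseline form at month 6 (5.3/5.4). Exponential PFS is an assumption.

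Expected number stopped before month 6 = 19 × [1 − 0.5^((6 − L)/m)], where m is the median and L the lag in months from first progression to the end of collection.

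With L = 0 (forms stop at first progression):
- m = 4.0: 19 × (1 − 0.5^1.5) = 19 × 0.646 = 12.3
- m = 4.6: 19 × (1 − 0.5^1.304) = 19 × 0.595 = 11.3

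Sections 4.2.1.1 and 6.1 require a second scan, more than 6 weeks later, before progression counts, and PFS is then backdated to the first scan. Collection may therefore run on to confirmation. The lag is applied to all events, although deaths would have none.

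| Lag | 6 − L (months) | m = 4.0 | m = 4.6 |
|---|---|---|---|
| 6 weeks | 4.62 | 10.5 | 9.5 |
| 8 weeks | 4.15 | 9.7 | 8.8 |
| 12 weeks | 3.23 | 8.1 | 7.3 |

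The expected number with only a baseline form is thus about 11-12 of 19 without a lag and about 7-10 with a 6-12 week lag. If the combination doubled median PFS to 8-9.2 months (assumption), the same formula gives 6.9-7.7 without a lag and 4.1-6.3 with one.

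**3. Quality-adjusted survival.** Forms at months 0, 6 and 12 can be interpolated, so six-monthly frequency alone does not prevent the 10.3 calculation. The gap arises when no form follows: after the stopping event, or after nivolumab discontinuation.

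**The case against.** Several points on the other side stand. Sections 6.3.1, 6.3.2 and 10.1 broadly agree with one another, so 5.3 and 5.4 could be read as the outliers; with visits every 8 or 9 weeks, all six GEE times then have a form within about a month. Section 5.1.14.2 calls week 8 (±2 weeks) the first follow-up visit, which makes a week-8 form more plausible under 6.3. The GEE is to use all available data, so it would run with fewer points. Section 1.6 limits these outcomes to description.

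This does not remove the conflict. Section 5.1.15 sends staff to 5.4, and using available data does not create forms that nobody is told to collect. A description of the patients who have not progressed is still selective.

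Two stronger readings are tempting and not supported. A reader might infer that a historical median PFS below 6 months guarantees at least 10 of 19 patients with only a baseline form, whatever the distribution. It does not: the count varies by chance (under the exponential model without a lag, the probability of 10 or more is 0.80-0.91), and the confirmation scan moves the median stopping time to 5.4-7.4 months. A reader might also infer that the planned analyses lack data under either schedule. For the 8-week and GEE analyses, that shortfall is certain only if 5.3/5.4 govern.

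**Conclusion.** The contradiction in timing is explicit and needs correcting. Under 5.3/5.4 the 8-week analysis has no scheduled post-baseline form and 2 of 6 post-baseline GEE times are collected; this rests on the text alone. Under 6.3 coverage runs from 4 to 6 of 6, depending on a visit interval that the protocol leaves open and on the ±1 month window assumed here.

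The stopping event is undefined for a patient and, on either reading, depends on outcome. Together with the absence of forms after nivolumab discontinuation, it is the cause of the gap in quality-adjusted survival; the six-monthly frequency is not. The counts of 11-12 and 7-10 of 19 are expectations, conditional on the endpoint meaning progression, on PFS like the historical arm and on an exponential distribution.

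The weight is moderate. HRQoL is a secondary objective, cost-utility is exploratory, both are meant for description, and the primary response-rate test is unaffected.

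**What to change.** - Put one schedule in 5.1.15, 5.3, 5.4, 6.3 and 10.1. The lightest adequate version keeps the six-monthly forms and adds a set at the 8-week follow-up, where the cost questionnaire is already given (5.4). Year 1 is then baseline, week 8, month 6 and month 12.
- Fit the GEE on actual assessment times, or on the times collected.
- Replace the stopping phrase in 5.3, 6.3.1 and 6.3.2 with collection to the one-year horizon of 10.2, death or withdrawal, regardless of response, progression or nivolumab discontinuation. Add the forms to the discontinuation visit in 5.3.
- In 10.3, state how utility after the last form is handled, with one sensitivity analysis under a different assumption.
- Editorial: five levels on five dimensions give 5^5 = 3,125 health states; the 243 in 6.3.2 is 3^5.

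**Cost.** Wording changes, plus one further form set per patient compared with 5.4, about 20 minutes at the protocol's own times (FACT-G up to 10, FKSI up to 5, EQ-5D about 5), and the forms added after discontinuation. Compared with 6.3, the light schedule has three post-baseline sets in year 1 instead of four to six.

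**Downsides.** The light schedule gives fewer GEE times than 6.3.1 lists. Some forms after discontinuation will still be missing: one visit followed by annual contacts does not reliably supply a month-6 form.

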6.3.2 EQ-5D

The EQ-5D is a patient self-administrated questionnaire that takes approximately 5 minutes to complete (See appendix D). The first part consists of 5 items covering 5 dimensions including: mobility, self-care, usual activities, pain/discomfort, and anxiety/depression. Each dimension can be graded on 5 levels. Health states are defined by the combination of the leveled responses to the 5 dimensions, generating 243 health states to which unconsciousness and death are added.

The 5-item index score is transformed into a utility score between 0, "Worst health state," and 1, "Best health state." The index score or the cost-utility equation can be used in the quality adjusted survival analysis depending on the health state(s) of interest.

Additionally the EQ 5D is utilized to establish health state utility which is used in cost-effectiveness analysis to calculate quality adjusted life years. This is the recommended health state utility form used in the United Kingdom and approved by the National Institute for Clinical Excellence (NICE) and has been used to establish health state utility and metastatic renal cell cancer patients. The EQ 5D will be given at baseline and at follow ups. The EQ-5D will also be available in the Spanish language.

The EQ-5D also includes a visual analog scale (VAS), a validated measure of general well-being, scored on a scale of 0-100. These data will be analyzed over time in a similar manner as the FACT-G and FKSI. EQ-5D will be collected prior to first Nivolumab dose (baseline), and at every subsequent follow up appointment until the patient meets primary endpoint.

6.4 Cost effectiveness data collection:

Healthcare utilization data needed to assess costs will be obtained from insurance claims and medical records. Also the cost effectiveness questionnaire will be completed by the patients at baseline, 8 week follow up and 6 months follow up (see Appendix G). These costs will be divided into the following domains:

Hospitalizations: For hospitalizations with physician billing records, inpatient physician costs will be estimated by applying Medicare payment rates under the RBRVS-based Medicare Fee Schedule to billed procedures in the physician billing records.

Radiation Treatment Cost: Direct costs of radiation treatment including consultation, simulation, treatment planning, and treatment delivery. Patient bills related to treatment will be obtained and estimated by total billed charges adjusted by facility-specific cost-to-charge ration from Medicare cost reports as described above.

Emergency Room visits: The date of ER visit and name of the facility, and whether the ER visit resulted in a hospital admission. ER costs will be estimated using

Medicare average payment rates for facility and physician charges, using the merged MEDPAR and MBS data as described above.

Physician and Clinic Visits: The date of the visit, the name of the physician or physician clinic, and the service provided (physician exam, lab test, physical therapy, etc.). Costs for physician and clinic visits will be calculated based on billing records obtained for such visits, using Medicare payment rates for procedures indicated in the clinic billing records.

Medications: Nivolumab is a new generation immunotherapy drug and is very costly (over \$100,000 per year). Nivolumab drug cost will depend greatly on the number of cycles received. Prescription drugs used, including information about name, dose, and frequency of all, will be recorded. The medications used by the study patients will be assigned an NDC drug code. Unit costs for these drugs will be estimated as the “AWP” price published in the Red Book less 15%. Outpatient drug costs will be calculated by multiplying unit cost by the number of pills used per day times the length of time the patient received the medication. Note that costs of drugs administered through a clinic (e.g., reimbursed under Medicare Part B) are included under “clinic visit costs” and inpatient drug costs are included under “inpatient facility costs.”

7.0 ADVERSE EVENTS

7.1 SABR

The contraindications and adverse events for SABR are mostly related to the treatment site and its radiation dose tolerance, as discussed in detail in section 4.1

7.1.1 Contraindications:

Treatment of patients who have received conventional radiation therapy at same site of new metastasis is at the discretion of the radiation oncologist. Treatment of patients who have received SABR at same site of new metastasis is contra-indicated. Treatment of patients with scleroderma or active Lupus is at the discretion of the radiation oncologist.

7.1.2 Special Warnings and Precautions for Use: N/A

7.1.3 Interaction with other medications: None

7.1.4 Adverse Reactions: Sites-specific. Please see section 4.1

7.2 Nivolumab

7.2.1 Contraindications

None

7.2.2 Special Warnings and Precautions for Use

See 7.2.4

7.2.3 Drug Interactions

No formal pharmacokinetic drug-drug interaction studies have been conducted with Nivolumab.

7.2.4 Adverse Reactions

In CA209001 (n = 39), in which subjects received a single dose of Nivolumab (BMS-936558) with possible retreatment at 3 months, the most frequent AEs were fatigue (56%), nausea (44%), proteinuria (38%), constipation (33%), back pain (33%), dry mouth

(28%), vomiting (28%), rash (26%), and dyspnea (26%). There was no clear or consistent relationship between the incidence or severity of AEs and the Nivolumab (BMS-936558) dose level (0.3, 1, 3, or 10 mg/kg IV single dose, with possible retreatment at 3 months). Of 39 (100%) subjects who had at least one AE, 32 (82%) had Grade 3 or 4 AEs regardless of causality. Three treatment-related SAEs were reported: hypothyroidism (Grade 2), colitis (Grade 3), and anemia (Grade 2). Among 12 deaths, none were considered drug-related.

In CA209003 (n = 296), as of the database lock date of 24-Feb-2012, BMS-936558-related AEs of any grade occurred in 70% of subjects. The most frequent drug-related AEs occurring in $\geq 5\%$ of subjects included fatigue (24%), rash (12%), diarrhea (11%), pruritus (10%), nausea (8%), decreased appetite (8%), hemoglobin decreased (6%) and pyrexia (5%). The majority of events were low grade, with Grade 3/4 drug-related AEs observed in 14% of subjects. The most common Grade 3/4 drug-related AEs occurring in $\geq 1\%$ of subjects were fatigue (2%), pneumonitis (1%), hypoxia (1%), diarrhea (1%), colitis (1%), abdominal pain (1%), AST/ALT increased (1% each), blood alkaline phosphatase increased (1%), lipase increased (1%), pneumonia (1%), hypophosphatemia (1%), and lymphopenia (1%). Drug-related serious AEs (SAEs) occurred in 11% of subjects. Grade 3/4 drug-related SAEs occurring in $\geq 1\%$ of subjects were: pneumonitis (1%), pneumonia (1%), lipase increased (1%), and diarrhea (1%). The spectrum, frequency, and severity of BMS-936558-related AEs were generally similar across dose levels and histological subtypes. Other drug-related AEs included vitiligo, hepatitis, hypophysitis, and thyroiditis. Hepatic or gastrointestinal events were managed with treatment interruption and administration of corticosteroids, and were generally completely reversible. Endocrine events were managed with replacement therapy. Several subjects in these categories successfully reinitiated treatment with BMS-936558. Drug-related pneumonitis occurred in 3% of subjects; Grade ≥ 3 pneumonitis developed in 3 subjects (1%). No clear relationship between the occurrence of pneumonitis and tumor type, dose level, or the number of doses received was noted. Early-grade pneumonitis was generally reversible with treatment discontinuation and corticosteroid administration. In three subjects, infliximab and/or mycophenolate were utilized for additional immunosuppression, with unclear effectiveness. There were three (1%) drug-related deaths due to pneumonitis. In two of these cases, the subject did not receive the early and aggressive intervention (including systemic corticosteroid therapy) that is likely key in the management of this toxicity, while in the third case, other anti-cancer agents (erlotinib and vinorelbine) may have contributed to the fatal event. Preliminary new non-clinical safety findings of adverse pregnancy outcomes and infant losses in the absence of overt maternal toxicity have been reported. The findings of increased late stage pregnancy loss and early infant deaths/euthanasia in Nivolumab exposed pregnant monkeys suggest a potential risk to human pregnancy if there is continued treatment with Nivolumab during pregnancy.

Opportunistic Infections Related to Immunosuppression

As of 03-Apr-2013, three subjects on Nivolumab (BMS-936558) clinical trials have developed opportunistic infections (2 cases of *Aspergillus*, and 1 case of *Pneumocystis jiroveci*) after receiving prolonged treatment with high dose steroids for Nivolumab-related adverse events without antifungal prophylaxis. Details of these cases are available in the BMS-936558 Investigator Brochure. Because of the potential for opportunistic infections with prolonged high dose corticosteroid administrations, the following recommendations should be considered for subjects with inflammatory events expected to require more than 4 weeks of corticosteroids or other immunosuppressants:

- Antimicrobial/antifungal prophylaxis per institutional guidelines to prevent opportunistic infections such as *Pneumocystis jiroveci*, bacterial and fungal infections.
- Early consultation with an infectious disease specialist should be considered.

Depending on the presentation, consultation with a pulmonologist for bronchoscopy or a gastroenterologist for endoscopy may also be appropriate.

- In addition, a concomitant opportunistic infection should be considered in the differential diagnosis when patients develop recurrent adverse events in the setting of ongoing or prior immunosuppressive use.

